10.4.1 Datasets to be analysed, analysis populations

Data from participants who completed the study will be analysed. Drop out data will be used only for descriptive purposes.

10.4.2 Primary Analysis

[name] will perform the primary analyses.

10.4.3 Safety analysis

The investigator will assess the feedback from the participant about the tolerability of the protocol.

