KlinV	Verordnung über klinische Versuche in der Humanforschung (in English: ClinO, in French OClin)
LRH	Loi fédérale relative à la recherche sur l'être humain
MD	Medical Device
OClin	Ordonnance sur les essais cliniques dans le cadre de la recherche sur l'être humain (in German : KlinV, in English : ClinO)
PI	Principal Investigator
RMSDD	Root-mean square differences of successive R-R intervals
RSA	Respiratory sinus arrhythmia

STUDY SCHEDULE

Study Periods	Screening	Treatment, Intervention Period		
		Pre	Middle	Post
Visit				
Time in days postnatal	3 ± 2	7	14 ± 3	21 ± 3
Patient Information and Informed Consent	x			
Demographics	x			
Medical History	x			
In- /Exclusion Criteria	x	x		
Medical Device		x	x	x
Primary outcomes: acceptability of the protocol, acceptability of the intervention, compliance, satisfaction with the intervention.				x
Secondary outcomes: heart rate variability, perceived stress, anxiety, depression.		x		x
Concomitant Therapy		x	x	x
Adverse Events		x	x	x

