3.4 Safety Objectives

The study aims to assess the safety and tolerability to use HRVB in such context.

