4.3 Safety Outcomes

The safety outcome variables will consist in tolerability of the procedure.

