8.2.3 Assessment of safety outcomes

Adverse events will be monitored during the training phase. The participant will keep a diary marking any negative events related to the HRVB program. As the program consists of a simple breathing technique, the risk that an adverse event would occur is low. At each session (before the HRVB program and after one week), the trainer will discuss with the participant adverse events that might have occurred. The participant will also have the opportunity to report adverse events by responding to the daily program reminder that she will receive by text message.

Tolerability of the HRVB protocol will be assessed at the end of the study by a qualitative interview.

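### Safety is a stated objective and adverse events are collected, but 4.3 and 10.4.3 pre-specify no adverse-event outcome or summary, and the sections disagree on whose data count

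*Combined protocol and SAP*

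**What the plan says.** Section 3.4 states the safety objective in two parts: "The study aims to assess the safety and tolerability to use HRVB in such context". Section 4.3 then defines the outcome more narrowly: "The safety outcome variables will consist in tolerability of the procedure". The safety analysis in 10.4.3 is a single sentence: "The investigator will assess the feedback from the participant about the tolerability of the protocol".

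Data collection is wider than either of these. The Study Schedule has a row "Adverse Events", marked at Pre, Middle and Post but not at Screening. Section 8.2.3 opens with "Adverse events will be monitored during the training phase" and names three routes: a diary, replies to the daily text reminder, and contact with the trainer ("At each session (before the HRVB program and after one week), the trainer will discuss with the participant adverse events that might have occurred"). It treats tolerability separately: "Tolerability of the HRVB protocol will be assessed at the end of the study by a qualitative interview".

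On who is analysed, 10.4.1 says "Data from participants who completed the study will be analysed. Drop out data will be used only for descriptive purposes". Section 10.5 restricts analysis to completers. Sections 6.3 and 7.4 say that acquired data will be analysed, including data from mothers who withdraw or do not comply. Section 8.2.4 offers drop-outs an interview and sends acquired data into the grant proposal.

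**The concern.** The chain from objective to outcome to analysis breaks for safety. Events are gathered by several routes, yet the plan does not say how they will be counted, graded, attributed to the program or summarised, or in which mothers. A team following 10.4.3 to the letter could base its safety statement on the investigator's impression of feedback in an open-label study, with no event count beside it.

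This matters because the study is meant to supply preliminary data for a larger project (2.3). Section 1.5 also promises annual safety reports, and 1.9 allows early termination if safety is in doubt or harm emerges, while 10.3 sets no statistical termination criteria and 11.3 plans no specific monitoring. A short event summary is the least that would support those provisions. With so few mothers, a report of no problems could also be taken as evidence of safety with nothing to show how little had been ruled out.

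**Working it through.** **1. Trace each half of the objective.**

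| Step | Safety (adverse events) | Tolerability |
|---|---|---|
| Objective, 3.4 | named | named |
| Outcome, 4.3 | not named | named |
| Assessment, 8.2.3 and Study Schedule | diary, trainer, text replies; Pre, Middle, Post | interview at study end |
| Analysis, 10.4.3 | none stated | investigator's assessment of feedback |

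Tolerability is carried through to an analysis. Adverse events stop at the assessment step. There is also a small mismatch: 8.2.3 places the trainer discussion at two sessions (before the program and after one week), while the schedule also marks the Post column.

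**2. Look for other text that fills the gap.**
- 10.4 covers acceptability, satisfaction, HRV and mental health symptoms. Adverse events are not mentioned.
- 7.4 says generally that everything acquired will be analysed. It sits under withdrawn participants and gives no method. The descriptive analyses it names concern baseline information and the amount of training.
- 9.1.1 and 9.1.2 deal with individual events: hazards needing measures are documented, and severe events go to the Sponsor-Investigator within 24 hours and to the ethics committee within 15 days. That is case reporting, not a study-level summary.

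**3. Compare the population rules.**

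| Section | Mothers who stop or do not comply |
|---|---|
| 10.5 | not analysed; missing data documented |
| 10.4.1 | used descriptively only |
| 6.3 | below the minimum sessions: excluded from analyses, yet the acquired data are to be analysed; withdrawn consent: analysed, for the drop-out rate |
| 7.4 | counted as drop-outs; all acquired data analysed |
| 8.2.4 | interviewed if willing; acquired data described in the grant proposal |

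These do not yield one safety denominator.

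**4. What a count in 10 mothers could show.** The plan gives no safety figure, threshold or precision, so there is nothing to reproduce. I take n = 10 from 10.2 and use exact binomial (Clopper-Pearson) limits.
- 0 of 10, two-sided 95% upper limit: 1 − 0.025^(1/10) = 0.308. One-sided: 1 − 0.05^(1/10) = 0.259.
- 1 of 10, two-sided 95%: 0.0025 to 0.445, that is 0.3% to 44.5%.
- No events in the analysed mothers if, as an assumption, only 8 or 7 are counted: 1 − 0.025^(1/8) = 0.369 and 1 − 0.025^(1/7) = 0.410.
- Chance of seeing no event in 10 at an assumed true risk of 10% per mother: 0.9^10 = 0.349. At 20%: 0.8^10 = 0.107.

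These numbers describe a sample of 10, with or without an event table. They do not measure the cost of the omission. They show what a safety statement should say about its own precision.

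**The case against.** The strongest reply is that this is loose wording in a very small study. Section 8.2.3 is headed as the assessment of safety outcomes and begins with adverse events, so the protocol evidently regards them as part of safety. Section 10.4.3 sets no time limit on the feedback, and diary entries, trainer discussions and text replies are all feedback from the mother. Severe events are reported separately. The device is CE-marked and Category A, 8.2.3 calls the risk low, and safety is neither the primary nor a secondary objective.

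Much of this stands, and it limits the point. It does not remove it: 8.2.3 gives adverse events and tolerability different methods, 10.4.3 names only tolerability, and no section specifies an event summary.

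A reader might go further and infer any of three things that the documents do not support.
- **That the safety objective cannot be answered.** The tolerability half is covered, and the event data will exist and can be described.
- **That a mother who has an event and stops is lost.** Sections 6.3, 7.4, 8.2.4 and 10.4.1 keep her data at least descriptively. The fault is that 10.5 contradicts them.
- **That the wide limits call for more mothers.** They follow from a feasibility sample of 10, and nothing here argues for changing it.

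**Conclusion.** The point holds in a limited form. The safety part of objective 3.4 has no pre-specified outcome in 4.3 and no pre-specified analysis in 10.4.3, although adverse events are collected. The population in which they would be summarised is contradictory across 6.3, 7.4, 10.4.1 and 10.5.

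This is minor to moderate. It rests on the text alone and on no assumed event rate. The figure of about 31% assumes that all 10 mothers are counted and that a two-sided 95% limit is used. No change in sample size, data collection or conduct follows from it.

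**What to change.** - **4.3:** extend the safety outcome to adverse events and tolerability.
- **10.4.3, population:** include all mothers who began any study procedure, whether the Pre assessment or training, and whether or not they completed. Starting the count at the first training session would miss a mother who had an event at the Pre assessment and left. The schedule collects events there, and 2.6 names the HRV measurement and the questionnaires as possible burdens.
- **10.4.3, content:** report the number and proportion of mothers with at least one adverse event, with an exact 95% confidence interval; a plain listing or count of events by seriousness and relatedness; and the number of mothers who stopped because of an event. Give the tolerability interview alongside. Intervals for every sub-count are not needed.
- **10.4.1 and 10.5:** exempt safety from the completers-only rule, and bring 6.3 and 7.4 into line.
- **Precision:** state that zero events in 10 mothers would exclude only rates above about 31% (two-sided 95%).

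The cost is a few sentences and one small table from data already to be collected. The downside is a less reassuring safety statement.

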10.5 Handling of missing data and drop-outs

We will analyze data only from participants who completed the study. Missing data from drop out participants will not be replaced but it will be documented.

11. QUALITY ASSURANCE AND CONTROL

11.1 Data handling and record keeping / archiving

Signed informed consent forms along with all physical documentation yielded by participants of this study will be kept in a locked cabinet in a locked room at the Research Unit of the Child and Adolescent Psychiatry Department of CHUV. Participants will be referred by a personal study code, without any personal information that could identify them (i.e., no names, no date of birth). The correspondence between the participant's identity and code will be known only by the principal investigator. CRF data will be first recorded on paper and then entered in an electronic database for analyses (double-check on data entry, by a research collaborator of the research unit, will be conducted to assure correctness).

11.1.1 Specification of source documents

The CRF of the participant will be the source data which will be kept in the research unit of Child and Adolescent Psychiatry Department. Questionnaires assessing stress and mental health will be kept in the research unit of Child and Adolescent Psychiatry Department.

11.1.2 Record keeping / archiving

All study data will be archived for a minimum of 15 years (according to local legislation) after study termination or premature termination of the feasibility study. Storage will be handled as described in section 12.1.

11.2 Data management

Data entry into Excel will be double checked (research collaborator from the research unit). Before the inferential statistical analyses, descriptive analyses will be conducted to verify the range of values.

11.2.1 Data Management System

The paper CRF will be entered and then managed on Excel for this feasibility study.

11.2.2 Data security, access and back-up

The data will be saved in a secured database on CHUV's server. The data will be accessible to the research team (members as defined in section 1).

11.2.3 Analysis and archiving

The paper data (consent form) will be stored and archived at the Research Unit of Child and Adolescent Psychiatric Department during the legal period of time (15 years).

11.3 Monitoring

No specific monitoring is planned for this feasibility study.

11.4 Audits and Inspections

The study documentation and the source data/documents are accessible to auditors/inspectors (also CEC and CA) and questions are answered during inspections. All involved parties must keep the participant data strictly confidential.

11.5 Confidentiality, Data Protection

The data will be directly coded (e.g. HRVB_001). The data will be protected and direct access to source documents will be permitted for purposes of audits and inspections (12.4). The data will be accessible only to the members of the research team (as defined in section 1).

11.6 Storage of biological material and related health data

No biological material will be collected. Health data provided in the CRF will be stored in the Research Unit.

12. FUNDING AND SUPPORT

12.1 Funding

This study will not be externally funded.

13. INSURANCE

As the study refers to risk category "A" no specific insurance will be contracted.

